Regarding the pain experienced during caries removal, several studies concluded that chemo-mechanical caries removal is more accepted, less painful technique of caries removal allowing patient to participate positively during dental treatment compared to the surgical method (Soni et al., 2015, Goomer et al., 2013, Pandit et al., 2007, Kochhar et al., 2011, Rafique et al., 2003). This finding could be attributed to many factors. Anusavice and Kincheloe (1987) explained absence of pain or mild pain sensation associated with chemo-mechanical caries removal because only carious dentin is removed in contrast to the conventional surgical method that includes removal of both sound and carious dentin. In addition, chemo-mechanical agents are available in form of gel covering the cavity that can provide thermal insulation during the caries removal. Meanwhile, no vibration or heat generation during the use of chemo-mechanical method resulting in no or little opening of dentinal tubules that can be account for minimal pulpal response. Munshi et al. (2002) mentioned that chemo-mechanical caries removal does not persuade pain and anxiety because it does not call for the use of local anesthesia thus avoiding the trauma associated with the injection and the fear of the needle.

[figure not shown]

Figure 1: Sodium hypochlorite-based chemo-mechanical caries removal agents.

Papacárie
 
The gel composition basically contains papain, an endoprotein extracted from papaya, chloramine, thickener and toluidine blue.
 
These components confer antibiotic, bacteriostatic and anti-inflammatory properties to this agent.
 
Papain acts only upon damaged tissues, since plasma antiprotease is not present in the infected tissue, preventing papain's proteolytic action in tissues considered normal.
 
Chloramine is a compound containing chloride and ammonia with antibiotic and disinfecting properties used for irrigation of root canals.
 
Toluidine blue is a photosensitive pigment that fixates to the bacterial membrane.
 
Advantages:
 
Low cost, an easy to apply material, which does not require technological devices in order to proceed to the chemical-mechanical removal of atraumatic caries, making the infected dentin more softened, which facilitates its removal with the use of non-cutting instruments and without anesthesia and rotary instruments.
	2003	

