The disadvantages accompanied with the use of the conventional surgical method of caries removal has been overcome by the use of “chemo-mechanical caries removal method”. “Chemo-mechanical caries removal” is one of the minimally invasive techniques that found to be less painful, less destructive and more accepted by children (Goomer et al., 2013, Soni et al., 2015). In addition to these advantages, the research holds clinical significance as a novel agent for “chemo-mechanical caries removal” (BRIX3000[®]) by the laboratory Brix Medical Science. It has been released recently in the dental market in 2015. It is a papain-based gel derived from leaves latex and fruits of green papaya (Carcia Papaya) that works as chemical debridement. It is for atraumatic caries removal with unique technology Encapsulating Buffer Emulsion (EPE) (Felizardo et al., 2018). This technology, according to the manufacture, provides the product with:

1. Proteolytic enzymatic activity that differs than previous products (Carie-Care) in the amount of papain used (3,000 U/mg in a concentration of 10%).
2. Perfect pH that solidifies the enzymes and set them free instantly on the collagen through its proteolytic activity.
3. Stable in room temperature with no need to be refrigerated with increased its shelf-life up to 48 months.
4. Increased enzymatic selectivity to damaged collagen.
5. Reduced time needed for removing the damaged dentinal tissues.
6. Enhanced the antifungal, antibacterial, and antiseptic ability.
7. Increased roughness to the cavity floor that favored better adhesion of the restoration.

By reviewing the literature, there are limited studies concerning its implementation in the area of pediatric dentistry. Clinical and microbiological studies are needed to confirm

manufacturer's claims by comparing this novel chemo-mechanical agent (BRIX3000[®]) and the previously-available chemo-mechanical agent (Carie-Care[™]) to the conventional surgical method for caries removal. Therefore, the purpose of this research is to perform clinical and microbiological evaluation of caries removal using these three different methods of caries removal in primary molars.

RESEARCH OBJECTIVES

- 1) To compare the efficacy of the chemo-mechanical method (BRIX3000[®], Carie-Care[™]) versus the conventional surgical method in decreasing the cariogenic bacteria in dentine caries of primary molar teeth in vivo.

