- 2) To compare the efficiency of the chemo-mechanical method (BRIX3000[®], Carie-Care[™]) versus the conventional surgical method in caries removal of primary molar teeth in vivo.
- 3) To compare the pain experienced by children during dental treatment with the chemo-mechanical method (BRIX3000[®], Carie-Care[™]) versus the conventional surgical method in caries removal of primary molar teeth in vivo.

HYPOTHESIS

The null hypothesis for this research will be as follows:

There is no difference in the efficacy, efficiency and pain experienced between chemo-mechanical caries removal agents (Brix3000[®]), (Carie-CareTM) and the conventional surgical methods in primary molars.

RESEARCH MATERIALS AND METHODS

This study will be carried out at King Abdulaziz Dental University Hospital (KADUH) and at Microbiology Research Laboratory in the Faculty of Pharmacy, King Abdulaziz University in Jeddah, Saudi Arabia to evaluate the efficacy, efficiency, pain experienced by children with the use of the chemo-mechanical method (BRIX3000[®]) and (Carie-Care[™]) versus the conventional surgical method in primary molars.

Materials:

Ethical Approval

The study was approved by the “Research Ethics Committee” at Faculty of Dentistry, King Abdulaziz University (KAU), under approval number 107-06-19.

Informed Consent

Written informed consent will be received from the parents or the guardians of the children after explaining the research procedures to them.

Subjects (sampling)

The study sample will consist of healthy and cooperative children between the ages of 4-9 years with bilateral open occlusal carious lesions in primary molars, who will attend as outpatients to the Department of Pediatric Dentistry at KADUH during the period from October 2019 to October 2020.

Inclusion criteria:

- Healthy and cooperative patients of age group 4-9 years.
- Primary first/second molars with open occlusal carious lesion having moderated depth and clinically visible brownish color softened dentin.
- No clinical signs or symptoms of pulp degeneration, such as tenderness to percussion and history of sinus tracts or swelling. Intraoral periapical radiographs with lesions having radiolucency extending into, but only confined to dentin.

Exclusion Criteria:

- Patients with any major and minor systemic illness.
- Uncooperative patients that necessitate pharmacological dental treatment.

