- Primary molars with mobile teeth, arrested caries, restored teeth, non-vital teeth, no carious lesion, presence of developmental defects and non-restorable teeth.
- Patients on any antibiotic regimen either on the day of treatment or for at least 2 weeks prior to the study.
- Patients allergic to Latex.
- Radiographic evidence of external or internal root resorption, furcal or periapical radiolucency.
- Primary molars with more than half of the root length resorbed.
- Children who did not attend and complete the second session of treatment.
- Not approving to sign the consent.

Sample Size Calculation:

The sample size was measured using G power analysis for calculating estimated sample size.

Based on the results of Bohari et al. 2012, it was found that 30 subjects per group were required

to detect a statistically significant difference between the two groups anxiety score (FLACC) with a power of 95% at the significance level of 0.05.

The study group will be consisted of 120 primary molars with bilateral design from 60 children aged 4-9 years without sex predilection. The included teeth will be assigned randomly into one of the following groups according to the decay removal technique that will be utilized using two-arm parallel groups with split-mouth design:

The control group (A): (n=60) primary molars will be subjected to removal of caries using a conventional drilling method using carbide dental burs.

The test group (B): (n=30) primary molars will be subjected to removal of caries using a chemo-mechanical agent (Brix3000[®], Brix Medical Science, Carcarañá-Santa Fe, Argentina).

The test group (C): (n=30) primary molars will be subjected to removal of caries using a chemo-mechanical agent Carie-Care[™], Uni-Biotech Pharmaceuticals Private Limited, Chennai, India in collaboration with Vittal Mallya Scientific Research Foundation).

Armamentarium & Equipment

- 1) Basic dental examination Kit
- 2) Restorative kit
- 3) Brix3000[®] “Brix Medical Science, Carcarañá-Santa Fe, Argentina”
- 4) Carie-Care[™] “Uni-Biotech Pharmaceuticals Private Limited, Chennai, India in collaboration with Vittal Mallya Scientific Research Foundation”.
- 5) Dental bur “Low-Speed Tungsten Carbide round bur US-NO 1-8, Meisinger, USA. L.L.C., [name]; High-Speed Diamond round medium size 08-018, Meisinger, USA. L.L.C., [name]”

- 6) Rubber dam kit.
- 7) Sterile vial.
- 8) Bacteriological incubator

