To assess the efficacy of caries removal in all groups, the outer surface of the decayed lesion will be washed with sterile normal saline (5 mL) to avoid contamination of plaque bacteria before taking the sample. The first sample will be taken from superficial carious lesion with the aid of a sterile sharp spoon excavator (Size #4; Nordan Manufacturing Inc., [name]). After completing caries removal, the cavity will be washed with sterile normal saline (5 mL) and dried with a sterile cotton pellet. A second sample of dentin will be taken from different sites of the cavity including the walls and floor using a sterile sharp spoon excavator (Size #4; Nordan Manufacturing Inc., [name]). The first and second samples will be collected in screw cap sterile vials containing 1 ml of isotonic saline for microbiological evaluation. Following decay elimination by both techniques, cavities will be filled using Glass Ionomer restoration (GC Fuji IX GP[®]) according to manufacturer’s instructions. For Microbiological cultivation and evaluation, dentin samples of all groups will be processed in the Advanced Techniques Laboratory in Dental research within 2 hours of collection. The samples will be vortexed for 30 sec to remove the microorganisms from dentin. The samples will be then regularly watered to obtain a 10^4 , and a sterile loop full of sample (0.1 ml) will be collected and cultured with aseptic technique onto blood agar plates (Schaedler agar) by streaking method. Then, the plates will be incubated aerobically at 35°C for 24 hours. Using

colony counter, the total viable count (TVC) will be obtained and expressed as colony forming units “CFU” per ml of sample.

To determine the efficiency of caries removal in all groups, time will be recorded in seconds by using a stopwatch from the beginning of caries removal till the cavity is certain to be caries-free.

To assess the pain experienced throughout caries removal in all groups, the “Wong-Baker FACES® Pain Rating Scale” (Wong & Baker, 1988) will be utilized (Fig. 4).

Dental treatment will be accomplished according to the following steps:

- Local anesthesia will be used for all groups.
- Rubber dam isolation will be used for all groups.
- Caries removal will be done utilizing one of the 3 techniques as follows:

The Control Group: Caries removal using “conventional drilling method”

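### The only power statement (30 per group, 95%) is for a FLACC anxiety score the trial does not plan to collect; no measured outcome has a stated power and none is named primary

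*Combined protocol and SAP*

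**What the plan says.** All references are to the combined protocol and SAP.

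- **Sample Size Calculation.** This section holds the only power statement. Thirty subjects per group are said to be needed "to detect a statistically significant difference between the two groups anxiety score (FLACC) with a power of 95% at the significance level of 0.05", on the basis of an earlier clinical study of caries removal in primary teeth. It gives no mean, SD, standardised effect, test or sidedness. The same section sets out three groups: 60 drilled molars, 30 treated with Brix3000 and 30 with Carie-Care, in 60 children with one pair of molars each.
- **Research Objectives and Hypothesis.** The first objective compares the gels "versus the conventional surgical method in decreasing the cariogenic bacteria in dentine caries of primary molar teeth in vivo"; the second concerns efficiency and the third pain. The null hypothesis is joint: "There is no difference in the efficacy, efficiency and pain experienced between chemo-mechanical caries removal agents" and conventional methods.
- **Clinical Procedures.** For efficacy, "the total viable count (TVC) will be obtained and expressed as colony forming units"; for efficiency, "time will be recorded in seconds by using a stopwatch from the beginning of caries removal". The sentence opening "To assess the pain experienced throughout caries removal in all groups" names the Wong-Baker FACES scale.
- **Literature Review.** This is the only other mention of anxiety. It reports that chemo-mechanical removal "does not persuade pain and anxiety because it does not call for the use of local anesthesia".
- **Statistical Analysis.** Paired and independent t-tests, or their rank equivalents, are to be used at 0.05. No outcome is named, no contrasts are listed and no adjustment is mentioned.

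**The concern.** A power figure has meaning only for a stated outcome, comparison and effect. Here the outcome is one the trial does not plan to collect. The comparison is between two unspecified groups out of three, with no indication whether it is paired. The effect is not given.

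A reader who sees 95% power may take a null result on bacterial count, time or pain as strong evidence of no difference, and nothing in the plan supports that reading. Because no outcome is primary, any of several nominally significant results could be presented as the main finding.

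**Working it through.** **1. Outcomes side by side**

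| Source | Outcome |
|---|---|
| Power statement | FLACC anxiety score |
| Objectives and hypothesis | Efficacy (bacteria), efficiency, pain |
| Procedures | Total viable count, seconds, Wong-Baker FACES |
| Statistical Analysis | None named |

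The first row matches none of the others. Pain is the nearest, but it is measured with a different named instrument, and nothing in the plan links the two scales.

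**2. Reproducing the stated 30.** This is not possible, because the difference, SD, test and sidedness are missing. The calculation can only be run backwards, to find the effect that 30 per group detects with 95% power.

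**3. Detectable effect, two-sided 0.05, no dropout (noncentral t)**

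- Gel against drilling, 30 pairs: df = 29, critical t = 2.045, noncentrality = dz × √30. Power of 0.95 is reached at dz = 0.681 SD of the paired difference. The normal approximation gives (1.96 + 1.645)/√30 = 0.66.
- Gel against gel, 30 against 30: df = 58, critical t = 2.002, noncentrality = d × √(30/2). Power of 0.95 is reached at d = 0.947 SD. The normal approximation gives (1.96 + 1.645) × √(2/30) = 0.93.

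The two SDs are on different scales, so 0.68 and 0.95 cannot be compared directly.

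**4. Power for assumed effects.** The plan gives no effect for any measured outcome, so this range is an assumption.

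| Assumed effect (SD on its own scale) | 30 pairs | 30 against 30 |
|---|---|---|
| 0.3 | 36% | 21% |
| 0.5 | 75% | 48% |
| 0.8 | 99% | 86% |

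**5. Effect detectable with 95% power if alpha is divided among contrasts**

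| Alpha | 30 pairs | 30 against 30 |
|---|---|---|
| 0.05 | 0.68 | 0.95 |
| 0.05/2 | 0.74 | 1.03 |
| 0.05/3 | 0.78 | 1.07 |

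A paired effect of 0.681 has 95% power at 0.05, 91% at 0.05/2 and about 87% at 0.05/3.

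**6. Lesser point: number of tests.** The plan lists no contrasts, so this count is derived. Three outcomes with two gel-against-drill contrasts give 3 × 2 = 6. Adding gel against gel, which the null hypothesis, the independent-sample tests and the Expected Findings section imply, gives 3 × 3 = 9. Before-and-after bacterial tests are also possible, since "A second sample of dentin will be taken from different sites of the cavity including the walls and floor", so nine is not a ceiling. If there are no true differences and the tests are independent, the chance of at least one false positive is 1 − 0.95^6 = 0.265 or 1 − 0.95^9 = 0.370. In simulation with assumed correlations of 0 to 0.8 between outcomes and 0 to 0.5 within child, it is about 19–27% for six tests and 22–36% for nine.

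**The case against.** The strongest reply concerns severity. No stated figure has been shown to be miscalculated, 30 per group may be enough, and the mismatch biases no estimate and changes no procedure. Sizing a trial on one outcome while measuring others might be called an omission rather than a contradiction. The flow diagram (Figure 3) and the opening pages were not available, so the absence of FLACC is established only for the text that was. All of this is fair. However, the sections where an outcome would be defined are present and omit FLACC, and a power claim tied to an outcome that is not planned is wrong as written.

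Three points on the figures stand as qualifications:

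- **Pooled reading.** The objectives can be read as comparing both gels together with drilling. With 60 pairs the detectable effect is 0.47 SD of the paired difference, and power at 0.5 SD is 97%. The null hypothesis and the Expected Findings section favour keeping the gels separate.
- **Rank tests.** If the non-parametric tests are used, the detectable effects rise to about 0.70 (pairs) and 0.97 (independent groups), using the asymptotic efficiency of 3/π.
- **Dropout.** Children who miss the second session are excluded, and no allowance is stated. With an assumed 27 per arm the figures are 0.72 and 1.00; with 24 they are 0.77 and 1.06.

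Leaving separately stated objectives unadjusted is a debated practice, so the multiplicity point would not on its own require a change.

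**Conclusion.** The concern holds and must be fixed. The stated 95% power applies to no outcome the trial plans to measure. None of the three measured outcomes has a stated power, and none is primary. The conclusion rests on comparing sections of the document and needs no assumed effect size.

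The sensitivity figures (0.68 SD paired, 0.95 SD between gels) show what the sample can detect under two-sided t-tests, complete data and separate gels. They do not show that 30 is too few or enough. The false-positive rates depend on assumed correlations and a derived count of contrasts, and they are secondary.

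**What to change.** 1. **Reconcile Sample Size Calculation with Clinical Procedures.** If FLACC was meant to be collected, add it to the objectives and procedures, and state the difference, SD, test and the two groups behind the 95%. Otherwise withdraw the FLACC power statement and write:

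   > Assuming two-sided t-tests and no dropout, 30 pairs (each gel vs drill) give 95% power at 0.05 for 0.68 SD of the paired difference, and 30 vs 30 (Brix3000 vs Carie-Care) for 0.95 SD. This describes the sensitivity of the sample and does not justify its size.

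   The rank-test and dropout figures can be added. A justification of the size would need a stated difference and SD for the chosen primary outcome.
2. **Name one measured outcome as primary, and list its contrasts, before outcomes are seen.** The choice is the sponsor's, since the plan does not rank them. For the two gel-against-drill contrasts, Holm at an overall 0.05 is a suitable choice; quote 0.74 SD of the paired difference (at 0.05/2). If gel against gel is included, apply Holm over three and quote 0.78 paired and 1.07 independent (at 0.05/3).
3. **Report the other two outcomes as secondary**, with 95% confidence intervals.
4. **If outcomes have already been seen**, report every contrast and state that no primary outcome was prespecified and that the FLACC-based power does not apply.

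If outcomes are unseen, the cost is wording only, with no extra children. The plan gives recruitment as October 2019 to October 2020 and does not show whether outcomes have been seen. The price is a less favourable power statement, and some p-values just under 0.05 would no longer be confirmatory.

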- 9) Inoculation loop.
- 10) Blood agar plates “Schaedler agar”
- 11) GC Fuji IX GP®.
- 12) A Stop Watch.

Methods:

Study design

Experimental, randomized controlled clinical trial with two-arm parallel groups and bilateral design following the “Consolidated Standards of Reporting Trials (CONSORT,2010)” statement (Fig.3).

Randomization

Since bilateral technique will be utilized in both parallel groups, it was decided to start on the right side irrespective of the method assigned by randomization. To control the variable of the side favored by the clinician, the researchers will make sure that each side is treated evenly by both methods using block randomization. Before recruiting participants, 60 sealed envelopes containing the randomization results will be arranged, sealed and mixed blindly in a box. Each envelope represents a block of the two contralateral teeth. The envelopes will be numbered blindly from 1 to 60. Each envelope will be opened immediately before starting the procedure on the right side.

[figure not shown]

Figure 3: Flow diagram of the Study

Clinical Procedures

The degree of dental destruction will be clinically determined by using a dental probe. Only open occlusal cavities with brown and softened dentin with broadly comparable depth exhibiting frank moderate cavitation will be chosen “severe decay, stage 5, ICDAS [International Caries Detection and Assessment System]” (Ismail et al., 2007, Dikmen, 2015). The depth of caries progression will be confirmed with an intraoral periapical radiograph such that radiolucency did not involve the pulp.

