The carious cavity will be treated with Carie-Care™ “Uni-Biotech Pharmaceuticals Private Limited, Chennai, India in collaboration with Vittal Mallya Scientific Research Foundation”. Following the instructions of the manufacturer, the Carie-Care™ gel will be brought to room temperature. The gel will be left in the carious lesion for 60 seconds. At that time, the appearance of the gel will be changed from translucent into cloudy. Then the gel will be removed with moistened cotton pellet and softened carious dentin will be scrapped off using spoon excavator ((Size #2, #3, #4; Nordent Manufacturing Inc., [name]). The process will be redone till consecutive administration of the gel was unsuccessful to turn into cloudy. Decay removal will be verified by probing with dental explorer (visual-tactile clinical criteria).

Statistical Analysis

The statistical assessment will be carried out using Statistical Package for Social Sciences (SPSS, V.20, IBM; Armonk, NY, USA). Analysis of data will be done through measuring *p*-value to determine statistical significance. The level of significance will be set at 0.05 (*p*-value of less than 0.05 was considered statistically significant). Various statistical methods will be used for measuring *p*-value depending whether the data will be normally distributed (parametric) or not normally distributed (non-parametric). For normally distributed data, paired sample t-test and independent sample t-test will be used. For non-normally distributed data, Wilcoxon signed rank test and Mann Whitney U test will be used.

Wong-Baker FACES® Pain Rating Scale

[figure not shown]

Figure 4: Wong-Baker FACES® Pain Rating Scale.

RESEARCH LIMITATIONS

Although, the chemo-mechanical methods cannot eliminate the dental caries completely, it tends to follow the principles of minimal intervention dentistry approaches. The generalization of results is one of the expected limitations of this research.

STRUCTURE OF THE RESEARCH

The research will be divided into several chapters:

- Chapter 1 will represent the introductory note on the state of dental caries among children and treatment approaches that are extensively used by the dentists including different chemo-mechanical agents used.
- Chapter 2 will present the literature review for the study.

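### Right-first order makes side and session one factor; the stated block does not guarantee that methods are balanced over sides, and the planned tests have no session term

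*Combined protocol and SAP*

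**What the plan says.** All references are to the combined protocol and SAP.

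- **Order** (Methods, Randomization): "it was decided to start on the right side irrespective of the method assigned by randomization".
- **Promise of balance** (same section): "the researchers will make sure that each side is treated evenly by both methods using block randomization".
- **Block** (same section): "Each envelope represents a block of the two contralateral teeth".
- **Envelopes** (same section): "60 sealed envelopes containing the randomization results will be arranged, sealed and mixed blindly in a box"; and "Each envelope will be opened immediately before starting the procedure on the right side".
- **Two sessions** (Exclusion Criteria): one criterion removes "Children who did not attend and complete the second session of treatment".
- **Numbers** (Sample Size Calculation): "The study group will be consisted of 120 primary molars with bilateral design from 60 children aged 4-9 years", with 60 drill teeth, 30 Brix3000 teeth and 30 Carie-Care teeth. That is 30 gel-versus-drill pairs per agent.
- **Analysis** (Statistical Analysis): "For normally distributed data, paired sample t-test and independent sample t-test will be used"; the rank versions (Wilcoxon signed rank, Mann-Whitney) are used for non-normal data. No term for side, session or order appears.

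The plan does not say how many envelopes put the gel on the right, overall or within each agent. Figure 3, the flow diagram, is not shown in the text available and may carry those counts.

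**The concern.** The right tooth is always first and the treatment has a second session, so the left tooth is the later one. Any difference between visits is then also a difference between sides. Self-reported pain and chair time in children aged 4–9 could plausibly change from one visit to the next.

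The promise of evenness concerns a count across children: how often the gel is used on the right. A block made of one child's two teeth does not constrain that count. If the count is uneven within a gel arm, part of the visit-to-visit change is added to the gel-versus-drill estimate for that arm. If it is even, the change cancels from the estimate but stays in the standard deviation that the paired test uses. The comparison of one gel with the other is exposed too, if the share of gel teeth treated first differs between agents.

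**Working it through.** **The plan's own figure.** The documents give no figure for balance over sides. The only related figure is 30 per group for 95% power at 0.05, and it cannot be reproduced because no effect size or SD is given. Back-solving for a two-sided paired t-test with 30 pairs gives a standardised paired difference of 0.68 (0.681 × √30 = 3.73; power 95.0%). I use this value as an assumption; it is not in the documents.

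**Model.** For each child in a gel arm let D = gel minus drill, with x = +1 if the gel was on the right (first) and −1 if on the left (second):

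D = δ + s·x + e, with SD(e) = 1.

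Here s is the first-minus-second difference in units of the SD of the paired difference. The documents give no value for it, so s from 0 to 1 is an assumed range. With n₁ gel-first and n₂ gel-second children, the mean of D estimates δ + s(n₁ − n₂)/n. The leak is 0.20 s at 18/12 and (20 − 10)/30 = 0.33 s at 20/10.

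**Chance of an uneven split in an arm of 30, under three readings of the box**

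| How the box was made up | Exactly 15/15 | 18/12 or worse | 20/10 or worse |
|---|---|---|---|
| 15/15 fixed within each agent | 100% | 0% | 0% |
| 30/30 fixed overall, not by agent (hypergeometric) | 20.3% | 19.6% | 1.9% |
| Side drawn independently per envelope (binomial) | 14.4% | 36.2% | 9.9% |

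Under independent draws, at least one of the two arms is 20/10 or worse with probability 1 − (1 − 0.0987)² = 18.8%.

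**Performance of the plain paired t-test** (simulation, 30 pairs, δ = 0 for type I error and 0.68 for power)

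| s | Exact 15/15: type I / power | Independent draws: type I / power | Given 20/10: type I |
|---|---|---|---|
| 0.3 | 4.0% / 94% | about 5% / 93% | 7% |
| 0.5 | 2.9% / 92% | about 5% / 90% | 10% |
| 0.8 | 1.2% / 86% | about 5% / 81% | 15% |
| 1.0 | 0.6% / 78–79% | about 5% / 72% | – |

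The first two columns differ for a reason. At exact 15/15 the session effect cancels from the mean and only the estimated SD is inflated, so the test is conservative. Under independent draws the mean itself varies with the split, so its variance is (1 + s²)/30. The standardised effect is then 0.681/√1.25 = 0.61 at s = 0.5 and 0.681/√2 = 0.48 at s = 1.

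**With a session term.** Type I error is about 5% throughout. Power is about 95% at 15/15 and about 94% under independent draws, whatever the value of s.

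**Dropout.** The envelope is opened before the first session, and children who miss the second are excluded. If 20% failed to return after drill first and 5% after gel first (assumed), 15/15 would become 12/14.25, a leak of 2.25/26.25 = 0.09 s even from a balanced box.

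**The case against.** The plan states its intention plainly and prepares 60 envelopes before recruitment, with 30 children per gel fixed in advance. That fits a box of fixed composition. A box holding 15 of each of the four possible cards would give exactly the promised evenness at full enrolment, and the missing flow diagram might show it. This stands. A reader might infer that the promised balance is not delivered, but the documents do not show that; they show only that the stated block does not guarantee it and that the composition is not given.

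A reader might also infer that always starting on the right biases the method comparison. It does not. Method is randomised to side, so the expected leak is zero, and under independent draws the overall type I error stays near 5%. The bias is conditional on an uneven realised split.

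The 9.9% figure rests on the least favourable reading of the box, so the range of 0% to 9.9% has to be quoted. The size of any session effect is assumed throughout.

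These points narrow the concern but do not remove it. Even a perfectly balanced box leaves the plain paired test conservative when a session effect exists, because the analysis ignores the factor that the design balances.

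**Conclusion.** The concern holds in a limited form. Side and session are one factor by design. The stated block does not by itself secure balance of methods over that factor, and no planned test accounts for it. The validity of the trial is not threatened: there is no systematic bias.

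What is at stake is precision and calibration. Power falls from 95% to 92% (balanced) or 90% (independent draws) at an assumed session effect of 0.5 SD, and to 78–79% or 72% at 1 SD. If an arm happened to split 20/10, type I error would be about 7%, 10% and 15% at 0.3, 0.5 and 0.8 SD. If there is no session effect, nothing is lost.

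These figures rest on the assumed standardised difference of 0.68, on the assumed session effects, and on taking the second session to be the left tooth's visit, which the fixed order implies but the plan does not spell out. The change is worth making because it is nearly free and delivers what the plan already promises.

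**What to change.** 1. State the composition of the box and fix it at 15 of each of four cards: Brix3000 right/drill left, drill right/Brix3000 left, Carie-Care right/drill left, drill right/Carie-Care left. Arranging them in permuted blocks of children (for example, random blocks of 4 and 8) would also keep the split close to even if recruitment stops short of 60. If the envelopes have already been used, report the realised counts by agent and side.
2. For approximately normal outcomes, analyse each within-child gel-versus-drill comparison with session (= side) as a term. Side and session stay inseparable, but the method estimate does not need them separated.
3. For non-normal outcomes, the Wilcoxon signed rank test cannot take such a term. Replace it with a test that respects sequence, for example a rank-sum comparison of first-minus-second differences between gel-first and drill-first children.
4. Report non-return by the method used first. The session term corrects the resulting imbalance, but not selection among those who return.

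The cost is the preparation of the envelope list, one degree of freedom, and a different rank test. If there is no session effect and the split is uneven, the term costs a little power: about 92% instead of 95% at 20/10. At 15/15 the loss is negligible.
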